- To investigate the chronic effects of exercise on maximal exercise capacity, this test will be performed: 1) at baseline; 2) after 8 weeks of normal lifestyle; and 3) after 8 weeks of exercise training.
- 6-min walk test. The purpose of this test is to assess the ability to walk for 6 min. The test will be completed at the subject's pace, walking back and forth between 2 cones. The objective is to walk as far as possible in 6 min. They will be permitted to slow down, to stop, and to rest, as necessary.
 - To investigate the chronic effects of exercise on walking ability, this test will be performed: 1) at baseline; 2) after 8 weeks of normal lifestyle; and 3) after 8 weeks of exercise training.
- Blood vessel tests. Our primary outcome is brachial artery FMD, an established non-invasive measure of endothelial function¹⁰. FMD will be determined via ultrasonography as we have previously described^{11, 12} and strictly conforming with established guidelines¹³. Arterial stiffness is known to influence FMD, therefore, it will be non-invasively measured using the SphygmoCor device as we have previously described¹⁴. Measures will be performed while subjects rest supine in a quiet, semi-darkened, temperature-controlled room. Individual subject data will be coded to ensure blinding during data analysis.
 - To investigate the chronic effects of exercise on blood vessel function, these tests will be performed: 1) at baseline; 2) after 8 weeks of normal lifestyle; and 3) after 8 weeks of exercise training.
 - To investigate the acute effects of HIIT on blood vessel function, these tests will be performed: 1) at rest; 2) at the end of a HIIT session; 3) after 1-hour recovery; and 4) after 24-hours recovery. To examine how chronic exercise training affects the acute responses of exercise, these tests will be performed at the beginning and end of the 8 weeks of exercise training.
 - To investigate the acute effects of maximal exercise on blood vessel function, these tests will be performed: 1) at rest; 2) at the end of the maximal exercise test on treadmill (described above); 3) at the end of the maximal exercise test on all-extremity cycle (described above); and after 1-hour recovery. To examine how chronic all-extremity exercise training affects the acute responses to maximal exercise test on all extremity cycle, these tests will be performed at the beginning and end of the 8 weeks of exercise training.

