
Visit 8 (3 hrs)
 
24-hr questionnaire
 
Weight
 
Maximal exercise test on all-extremity cycle
 
Pre-exercise, end and 1-hour post-exercise:
 
Blood pressure and heart rhythm
 
Blood vessel tests

All-extremity HIIT Practice
 
Prior to initiating the 8-week training program, a period of familiarization with all-extremity HIIT exercise will be provided. During this time, the exercise duration and pace will gradually increase with each session until subjects are able to complete the HIIT protocol.

Visit 9a (3 hrs)
 
24-hr questionnaire
 
Weight
 
Exercise session on all-extremity cycle
 
Pre-exercise, end and 1-hour post-exercise:
 
Blood pressure and heart rhythm
 
Blood vessel tests, intravenous catheter and blood draw

Visit 9b (1 hr)
 
24-hr questionnaire
 
Weight
 
Blood pressure and heart rhythm
 
Blood vessel tests and blood draw

8-week training period: 40 min/session scheduled every week on M, T, Th, F

Visit 10 (2.5 hrs) 24-hr questionnaire and activity monitor pick up Weight Blood pressure and heart rhythm Nitroglycerin test and intravenous catheter Intra-arterial catheter, cell collection and blood draw
Visit 11 (1 hr) Questionnaires Pregnancy test Weight, waist/hip circumferences and body composition scan 6-min walk test
Visit 12a (3 hrs) 24-hr questionnaire Weight Exercise session on all-extremity cycle Pre-exercise, end and 1-hour post-exercise: Blood pressure and heart rhythm Blood vessel tests, intravenous catheter and blood draw
Visit 12b (1 hr) 24-hr questionnaire Weight Blood pressure and heart rhythm Blood vessel tests and blood draw
Visit 13 (3 hrs) 24-hr questionnaire Weight Maximal exercise test on all-extremity cycle Pre-exercise, end and 1-hour post-exercise: Blood pressure and heart rhythm Blood vessel tests

These visits will be scheduled over 6-7 months which should alleviate some of the burden:

- 1) visits 1-5 will be scheduled over 2-3 weeks and will total 7.5 hours;
- 2) during the 8-week control period of normal lifestyle there will be no scheduled visits;
- 3) visits 6, 7, 8, 9a and 9b will be scheduled over 2-3 weeks and will total 10.5 hours;
- 4) during the 8-week exercise training period there will be 4 scheduled exercise sessions/week;
- 5) visits 10, 11, 12a, 12b and 13 will be scheduled over 2-3 weeks and will total 10.5 hours.

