Sample Size, Statistical Analyses, and Anticipated Results

Sample size justification. For power analyses, we set $\alpha=0.05$ and $\beta=0.80$ and used the smallest effect size (ES) based on our preliminary data on FMD, which is our primary outcome. To detect significant sex differences in acute/chronic FMD responses, we will need 11 men and 11 women (ES=1.57 for acute and 1.28 for chronic response). To detect

significant acute and chronic changes in FMD in response to NWA-HIIT in older men we will need 10 men (ES=1.02 for acute and 3.87 for chronic response). We anticipate we will need to consent and screen 165 research participants to meet the study inclusion criteria and obtain complete datasets in 11 men and 11 women.

Statistical analyses. Our primary outcome will be FMD. For both Aim 1 and 2, we will use mixed factorial ANOVA. Post hoc and multiple tests will be corrected using the Bonferroni adjustment. Secondary analyses will be performed using ANCOVA to account for influence of potential confounders. Exploratory analysis will evaluate the mechanisms by which exercise influences FMD and stimulate future mechanistic studies. Using linear regression, we will examine whether responses to acute NWA-HIIT are correlated with responses to chronic 8-week NWA-HIIT. Analysis of the RNA sequencing data will be conducted by the ICBR bioinformatics staff.

HUMAN SUBJECTS

Human Subject Characteristics

Subjects will be sedentary men and postmenopausal women recruited from the community using advertisements. Subjects will be screened by our experienced study clinicians with oversight by our cardiologist ([name]) according to the study inclusion/exclusion criteria based on the medical history, physical examination, general blood tests and diagnostic maximal exercise test.

Inclusion criteria

- adults able to give consent
- men and women
- women must be postmenopausal (either natural or surgical)
- 60 to 79 years of age

Exclusion criteria

- any relevant cardiovascular diseases (e.g., history of coronary artery bypass surgery or angioplasty, or heart failure, myocardial infarction, angina pectoris, peripheral arterial disease)
- myocardial ischemia during maximal graded exercise test
- major chronic clinical disease (e.g., diabetes, renal or hepatic disease or infection with hepatitis B, C, or HIV)
- seizures, or other relevant on-going or recurrent illness
- recent (within 3 months) or recurrent hospitalizations
- systolic blood pressure <100mmHg

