- body mass index > 35 kg/m²
- >5% weight change in past 3 months or unwilling to remain weight stable during study participation
- use of tobacco products including smoking traditional or e-cigarettes
- use of hormone replacement therapy in women or men (e.g., estrogen, progesterone or testosterone)

- regular aerobic exercise training (≥ 30 min/session and ≥ 3 days/week)

Informed Consent

Research volunteers who contact the PI's laboratory in response to our recruitment efforts (advertisements) will be asked to complete a phone screening or an online RedCap screening questionnaire to determine if they qualify to participate in the study. Volunteers who meet the preliminary inclusion criteria and are willing to participate will be given the consent form to read prior to obtaining written consent. Informed consent will be obtained by the PI, [name], or her research assistant, [name], in a quiet and private area or via a secure password-protected UF Zoom meeting. If consent is obtained via Zoom, then the subject's signature will be obtained using REDCap eConsent. All procedures and risks related with participation in the study will be described and the subject's understanding of the study will be confirmed. Any questions will be answered prior to obtaining the subject's written consent. The consent form will then be signed by both the subject and investigator as documentation of consent. Consent will be documented in the subject's research file. A copy of the signed consent form will be provided to the subject.

Compensation

Subjects will be compensated a total of \$360 for completing visits 5-13 in the form of a gift card upon completion of the study. In addition, for every week that a subject completes all 4 supervised exercise sessions s/he will be compensated an additional \$5 (e.g., a subject who completes 4 sessions/week for 8 weeks will receive an additional \$40, thus increasing the total compensation from \$360 to \$400). Payment will be given to subjects within a few weeks following completion of their participation or withdrawal from the study.

If subjects do not complete all visits, then compensation will be prorated according to the following plan:

Visits 1-4	Will receive the health screening results at no cost. No financial compensation will be provided.
Visit 5	\$45
Visit 6	\$10
Visit 7	\$45
Visit 8	\$25
Visit 9a	\$25
Visit 9b	\$10
Visit 10	\$75

Visit 11	\$10
Visit 12a	\$45
Visit 12b	\$20
Visit 13	\$50

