- Upon arrival at the Center for Exercise Science for a scheduled visit, participants will be screened for history and symptoms of COVID-19 and body temperature will be taken using a contactless forehead thermometer prior to exiting their car. If they answer yes to any of the screening questions and/or their temperature is greater than 100.4 degrees, then they will need to reschedule the visit. Participants will be given a surgical mask and a 2 oz. bottle of hand sanitizer. They will be asked to wear the mask and use the hand sanitizer prior to entering the building and frequently sanitize their hands during the visit and social distance whenever possible.
- During the pandemic, participants will complete a COVID-19 test 3-5 days prior to VO₂max testing and only those who are confirmed negative will proceed to complete the VO₂max test. The COVID-19 test will be prescribed as long as [name] deems it necessary and will be paid by the study.
- Exercise sessions will be performed at home and exercise supervision will be conducted remotely live via UF Zoom using a wearable device which provides real-time heart rate monitoring.

Specific risks associated with nitroglycerin: Risks related to nitroglycerin administration will be minimized by providing adequate clinical supervision and by taking the following safety precautions. An intravenous catheter will be inserted in a peripheral vein prior to nitroglycerin administration, in case the effect of nitroglycerin necessitates the administration of fluids or medication. ECG will be monitored continuously. Blood pressure will be monitored prior to nitroglycerin administration and post-administration as frequently as deemed necessary. For individuals whose systolic blood pressure is <100 mmHg, nitroglycerin will not be administered. Subjects will remain in bed for 30 minutes after nitroglycerin administration to allow blood pressure to return to baseline before ambulating. Nitroglycerin has been administered safely in our laboratory for more than 10 years, and in other laboratories, and clinical situations worldwide.

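### The planned ANOVA keeps only complete cases by default; a mixed model for Aim 1 and contrast-by-contrast inclusion for Aim 2 would use partial FMD data and limit completer selection, for a small gain in precision

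*Combined protocol and SAP*

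**What the plan says.** The Statistical analyses paragraph makes FMD the primary outcome and names one primary method: "For both Aim 1 and 2, we will use mixed factorial ANOVA". Post hoc and multiple tests get a Bonferroni correction. ANCOVA is mentioned only as a secondary analysis for confounders. No rule for missing data and no analysis population is given.

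The Sample size justification expects to screen 165 people to "obtain complete datasets in 11 men and 11 women", with effect sizes for the sex difference given as "ES=1.57 for acute and 1.28 for chronic response".

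Section 6 (Study design and timing of measures) asks for three FMD time points in Aim 1: baseline, after the control period and after training. Aim 2 asks for four in each of two training states. The procedures list the post-exercise scans as "2) at the end of a HIIT session; 3) after 1-hour recovery; and 4) after 24-hours recovery".

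Two places allow for visits that do not go to plan. Compensation says "If subjects do not complete all visits, then compensation will be prorated according to the following plan", with separate amounts for Visits 9b and 12b. The COVID-19 arrival screen says that if "their temperature is greater than 100.4 degrees, then they will need to reschedule the visit".

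In the visit list, the trained-state 24-hour scan has its own visit: "Visit 12b (1 hr) 24-hr questionnaire Weight Blood pressure and heart rhythm Blood vessel tests and blood draw". Visit 10 is the post-training counterpart of Visits 5 and 7. Its entry begins "Visit 10 (2.5 hrs) 24-hr questionnaire and activity monitor pick up Weight Blood pressure and heart rhythm Nitroglycerin test and intravenous catheter" and goes on to the arterial procedure. Unlike Visits 5 and 7, it lists no blood vessel tests.

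**The concern.** A classical mixed factorial ANOVA needs every within-subject cell filled. For Aim 1 that means 3 FMD values per person. For Aim 2 it means 4 x 2 = 8, or 4 per state if the states are analysed separately. A participant who misses only the 24-hour scan then drops out of the 1-hour minus rest comparison too, although that comparison does not use the missing scan. A 24-hour visit moved to another day is no longer a 24-hour scan, and the document does not provide for repeating the session.

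Two things are at stake. The first is precision: scans already paid for and taken are thrown away. The second is selection. A completers analysis of the chronic sex contrast is unbiased only if missingness is unrelated to FMD. A likelihood-based mixed model needs the weaker condition that missingness is explained by the scans that were observed.

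For Aim 1 it is also unclear which resting scan fills each time point, so it is unclear whose data count as complete.

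**Working it through.** **1. The plan's sample size.** Inputs are the stated effect sizes, alpha 0.05 and power 0.80 (the plan prints this as beta). The test is taken as two-sided, which the plan does not state. A two-sample noncentral t calculation gives:
- effect size 1.28: power 0.772 at 10 per sex and 0.815 at 11, so 11 per sex is reproduced;
- effect size 1.57: power 0.938 at 11 per sex.

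**2. Aim 2, at the plan's own target.** Take 11 + 11 completers plus k further participants of one sex who lack only a 24-hour scan. The values k = 1 to 3 are assumed. For 1-hour minus rest with equal SDs, the SE is proportional to sqrt(1/n1 + 1/n2). Using the k people changes it by the ratio

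sqrt(1/11 + 1/(11+k)) / sqrt(2/11) = 0.979, 0.961, 0.945 for k = 1, 2, 3.

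The SE therefore falls by 2.1%, 3.9% and 5.5%. If 1.57 applies to this contrast (assumed), power rises from 93.8% to 94.8%, 95.5% and 96.2%.

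**3. Aim 1, at the plan's own target.** Take 11 + 11 completers plus k women who have the first two scans but not the last. Assume equal variances and a common correlation rho between scans, with the covariance known. The first two scans explain a fraction f = 1/(2(1+rho)) of the variance of the final-minus-control change. The SE ratio is

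sqrt{[1 + (1-f) + f x 11/(11+k)] / 2}.

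| rho | f | k = 1 | k = 3 |
|---|---|---|---|
| 0.4 | 0.357 | 0.993 | 0.981 |
| 0.8 | 0.278 | 0.994 | 0.985 |

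The SE falls by about 0.6 to 1.9%, and by less once the covariance has to be estimated.

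**4. Aim 1, selective loss (illustration).** Suppose there is no true sex difference, and the 3 of 11 women with the lowest FMD after the control period lack the final scan. The 8 who remain have an expected standardised mean of 0.422 at that time point and regress downwards afterwards. In SD of change, the error in the contrast is

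(1-rho) x 0.422 / sqrt(2(1-rho)) = 0.23 at rho 0.4 and 0.13 at rho 0.8.

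This is 18% and 10% of the planned 1.28. It makes women's response look too small, so it inflates a men-minus-women difference. Simulated type I error of the completers t test is about 8% and 6% (100,000 runs each).

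An unstructured mixed model with Kenward-Roger degrees of freedom, fitted to all scans in the same illustration (10,000 runs per case), is off by at most 0.01 SD, with type I error of 5.2 to 5.6%.

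Recruiting to 11 completers does not remove the effect. If 14 women enter and the lowest 3 lack the final scan, the upper 11 have an expected mean of 0.347. The error is then 0.347 x sqrt((1-rho)/2) = 0.19 at rho 0.4 and 0.11 at rho 0.8.

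**5. Which resting scan.** Blood vessel tests appear before exercise or at rest at Visits 2 and 5 (baseline phase), 7, 8 and 9a (after the control period) and 12a and 13 (after training). Visit 9a follows the HIIT practice sessions, so it is not interchangeable with Visit 7. The procedures require a post-training measurement for the chronic question, but the list does not say which visit supplies it.

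**The case against.** The strongest reply is that the 11 + 11 are counted after incomplete participants have been set aside, from 165 screened. A reader might infer a power loss, for example that losing three women to a missed 24-hour scan leaves 11 v 8 and takes power at effect size 1.57 from 93.8% to 88.9%. The document does not support that reading: it describes a trial that stopped short of its own target. This objection stands, and it is why the gains in steps 2 and 3 are measured from 11 + 11 completers.

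Second, the evidence that scans will be missed is indirect. The payment table covers every visit from 5 to 13 and forecasts nothing. The arrival screen says to reschedule. That a moved 24-hour scan is lost is an inference from silence about repeating the session. This also stands, so the counts of 1 to 3 are illustrations.

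Third, the plan names a method and not a deletion rule. Its Bonferroni-corrected tests might already use all available pairs, and then the Aim 2 gain is already there. That is possible, but the text does not say so, and the target of complete datasets points the other way.

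Fourth, nothing in the document suggests that missingness depends on FMD. True; the selective-loss case shows what the completers analysis is exposed to, not what will happen.

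**Conclusion.** The point holds in a limited form, as an improvement worth making and not as a flaw that endangers the trial. If recruitment runs to 11 + 11 completers, planned power is intact. The remaining cost is discarded partial data: 2.1 to 5.5% of the SE for an Aim 2 two-scan contrast, and about 0.6 to 1.9% for the Aim 1 chronic contrast. There is also exposure to completer selection, worth 0.13 to 0.23 SD of change in the stated illustration. These sizes rest on assumed numbers of incomplete participants, assumed correlations of 0.4 to 0.8 and equal SDs. With complete data there is no gain.

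A reader might also infer from the quoted effect sizes that men's and women's responses differ in variance, and so fault the ANOVA on that ground. The plan does not define how those effect sizes were standardised, so they cannot show it.

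**What to change.** **Aim 1.** Make the primary analysis a linear mixed model with sex, time and sex x time, an unstructured covariance over the three times and Kenward-Roger degrees of freedom. Fit it to all available FMD scans from eligible participants who entered the control period. Keep the completers ANOVA as a sensitivity analysis.

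**Aim 2.** Keep the planned omnibus test. Run the planned Bonferroni-corrected sex contrasts on participants' own change scores, including everyone who has the scans that each contrast needs. Name the contrasts in advance and keep them few: at 11 per sex and effect size 1.57, power is 93.8% for one test, 84.6% for three and 76.4% for six. The plan already carries this correction, so it is not a new cost.

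**Scans.** State which visit supplies the resting FMD at each Aim 1 time point, and reconcile Visit 10 with the requirement for a post-training measurement.

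**Cost and limits.** The change is a few lines of analysis text and standard software, with no new measurements. On complete data the Aim 1 model gives the same chronic sex contrast as a pooled change-score t test on 20 df. The model's protection covers only missingness explained by observed scans, and someone who leaves before the trained state still contributes no post-training value. The Aim 2 contrasts recover people but do not correct for selective loss, and a missed pre-exercise scan still removes all three change scores in that state.

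### Holm's step-down adjustment could replace Bonferroni for the post hoc and multiple tests: same 0.05 familywise bound, at least as much power, but a gain only where several effects in a family are real

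*Combined protocol and SAP*

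**What the plan says.** The section on sample size, statistical analyses and anticipated results makes flow-mediated dilation (FMD) the primary outcome and gives the main model: "For both Aim 1 and 2, we will use mixed factorial ANOVA". It then gives one sentence on multiplicity: "Post hoc and multiple tests will be corrected using the Bonferroni adjustment". It does not say which tests form a family, how many there are, or whether the adjustment is single-step or step-down, and it does not limit the sentence to FMD. Bonferroni without qualification ordinarily means the single-step method.

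Several comparisons follow from the design. For the acute study, the blood vessel tests are done "1) at rest; 2) at the end of a HIIT session; 3) after 1-hour recovery; and 4) after 24-hours recovery", before and after training. For Aim 1 there are three occasions: baseline, after the control period and after training.

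The sample size rests on "11 men and 11 women (ES=1.57 for acute and 1.28 for chronic response" for the sex differences. For change within men the plan says "we will need 10 men (ES=1.02 for acute and 3.87 for chronic response". It makes no allowance for multiplicity.

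**The concern.** Single-step Bonferroni tests every hypothesis in a family of *m* at 0.05/*m*, even after others in the family have been rejected. Holm relaxes the threshold after each rejection and keeps the same familywise guarantee. With 11 people per sex and a sample size calculated at an unadjusted 0.05, there is no reserve to absorb a correction. More participants are expensive: the plan expects to consent and screen 165 people for 22 complete datasets. What is at stake is power for the follow-up comparisons that say when FMD changes and at which times the sexes differ.

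**Working it through.** **Inputs from the plan.** Alpha 0.05 (two-sided assumed, since that reproduces the stated numbers); power 0.80 (printed as beta); 11 per sex; effect sizes 1.57 (acute) and 1.28 (chronic) between sexes, 1.02 (acute) and 3.87 (chronic) within men.

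**Assumed, because the plan is silent.** The families, which effects are real, and the correlation between tests (0.5, with 0 as a check).

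**1. The plan's own figures.**
- Two-sample t test: noncentrality d√(n/2) = 1.28 × √5.5 = 3.00, 20 df, critical value 2.086, power 0.815. Ten per sex gives 0.772, so 11 is the smallest adequate number.
- Paired t test: d√n = 1.02 × √10 = 3.23, 9 df, critical value 2.262, power 0.818, so 10 men.

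Both stated numbers reproduce, at unadjusted 0.05.

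**2. The two rules.** Bonferroni rejects when p ≤ 0.05/m. Holm orders the p-values, compares the k-th smallest with 0.05/(m − k + 1), and stops at the first failure. For m = 3 the thresholds are 0.0167, 0.025 and 0.05.
- The first threshold is the same, so the chance of at least one rejection is identical.
- Later thresholds are larger, so Holm never rejects less.
- With m₀ true nulls, the first of them to be tested faces a threshold of at most 0.05/m₀. The chance of any false rejection is therefore at most m₀ × 0.05/m₀ = 0.05, under any dependence.

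**3. Bonferroni power, exact.**
- Paired, effect size 1.02, 11 men, m = 3: noncentrality 1.02 × √11 = 3.38, 10 df, critical value 2.870, power 0.691.
- Sex contrasts, 11 per sex, m = 2: critical value 2.423; power 0.716 for effect size 1.28 and 0.886 for 1.57.

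**4. Holm against Bonferroni.** Simulated t tests, 200,000 trials per row, 11 per sex, correlation 0.5.

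| Assumed family and real effects | Quantity | Bonferroni | Holm |
|---|---|---|---|
| Men, three acute comparisons with rest, all 1.02 | power per test | 69% | 79% |
| same | all three detected | 44% | 67% |
| Two at 1.02, one null | power per real effect | 69% | 74% |
| same | null rejected | 1.7% | 3.9% |
| One at 1.02, two null | power for the real effect | 69.1% | 69.3% |
| Sex contrasts 1.28 and 1.57 as a family of two | chronic power | 71.5% | 79.8% |
| same | acute power | 88.6% | 91.1% |
| same | both detected | 67% | 78% |
| Sex contrasts, only 1.28 real | chronic power | 71.5% | 71.6% |
| Men, Aim 1 phases: two at 3.87, control period null | power per real effect | 100% | 100% |
| same | null rejected | 1.7% | 5% |

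At correlation 0 the picture is the same: 69% to 81% per test in the first row, and 71.5% to 80.2% for the chronic sex contrast. In the last row the two large effects are always rejected, so Holm tests the remaining null at the full 0.05.

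**The case against.** The case for leaving the sentence alone is substantial, and most of it stands.

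- **Bonferroni is valid and pre-specified.** A reader might infer that the plan contains an error, or gives power away for nothing. It does neither: Bonferroni has simple simultaneous intervals that agree with its tests, and Holm does not.
- **Holm does not leave false positives unchanged.** Comparing the methods only when every null is true suggests so, because there they must agree. When some effects are real, Holm spends error that Bonferroni leaves unused, as the 1.7% to 3.9% row shows. The bound holds, but a given true null is rejected more often.
- **The largest gain is a favourable case.** It needs effect size 1.02 at end of exercise, 1 hour and 24 hours. The plan gives a single acute effect size for men, and its Background describes a transient fall in men that is absent in women. If only one time is affected, nothing is gained.
- **Aim 1 in men gains nothing.** At 3.87 power is already complete, while the control-period comparison, which is meant to reveal change due to measurement error, would be falsely rejected more often.
- **Reach is limited.** The sex-by-time test in the ANOVA is affected only if it counts among the multiple tests.
- **Holm is not the most powerful option either.** For comparisons with a common rest value under a normal model, step-down Dunnett would do better. It relies on that model, though, and Holm does not.

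What does not fall is the dominance result: at the same bound and with no added assumptions, Holm never rejects less.

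**Conclusion.** This holds as an efficiency improvement at almost no cost, and no further. Given the assumed families, 11 per sex and correlation 0.5, the gain is about 10 points per test if all three acute effects in men are 1.02, and about 4 if two are. It is about 8 points for the chronic sex contrast if that is paired with the acute contrast at the plan's own effect sizes. It is essentially nil if one effect is real or for the chronic change within men. None of these is the expected gain for this trial, because the documents define no family and do not say how many effects are anticipated.

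A reader might also infer that Holm restores the planned 80% power. It does so for the chronic sex contrast only in the assumed family of two with both effects real. The undefined family matters more than the choice between the methods: for effect size 1.28 with 11 per sex, a Bonferroni divisor of 2, 3 or 6 gives power 0.716, 0.652 or 0.541.

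**What to change.** Replace the Bonferroni wording with: *Holm step-down adjustment within each named family*, and list the families. Examples are the acute comparisons with rest for each sex, the acute sex contrasts, and the Aim 1 phase comparisons. State whether the untrained and trained acute series are separate families and whether the ANOVA interaction test belongs to any of them. Naming the families is worth doing even if Bonferroni is kept, because it fixes the divisor.

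The cost is a sentence or two and no extra data. Two consequences should be accepted openly. A true null is rejected more often when other effects in its family are real, still within 5%; the sponsor may weigh that for the control-period comparison. Any Bonferroni intervals shown beside Holm tests should be labelled conservative, since one may include zero for a Holm-significant result.
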